## 2.11 Patient-reported outcomes

The global health status/QoL score of the QLQ-C30 and PGIC score are identified as the primary PRO variables of interest. Physical functioning, emotional functioning and social functioning scale scores of the QLQ-C30 are identified as secondary PRO variables of interest. The FAS will be used for analyzing PRO data. Scoring of PRO data and methods for handling of missing items or missing assessments will be handled according to the scoring manual (see [\[study protocol Appendix 5\]](#)). No imputation procedures will be applied for missing items or missing assessments.

Descriptive statistics will be used to summarize the QLQ-C30 scores and absolute change from baseline scored scales by each scheduled timepoint and treatment arm.

Between-treatment differences for the change in QLQ-C30 scores will be evaluated using a mixed effect repeated measures model. Treatment group, stratification factors (FLT3 mutation status and chemotherapy regimen), time of visit (in weeks counting from the time of randomization to the time of a particular post baseline measurement in time windows), treatment by time of visit interaction, and baseline score. An unstructured covariance structure will be assumed for the model. The differences in least square means between treatment and control group, and the corresponding 95% CI at selected timepoints will be presented.

The PGIC score will be presented as frequencies and percentages by scheduled timepoint and treatment arm.

## **2.12 Biomarkers**

All [REDACTED] analyses other than baseline FLT3 mutational status and ELN 2017 AML risk classification will be reported in separate biomarker report with separate (stand-alone) analysis plan.

As a project standard, Novartis will analyze only biomarkers collected in the clinical database.

[REDACTED]

There may be circumstances when a decision is made to stop sample collection, or not perform or discontinue their analysis due to either practical or strategic reasons (e.g. issued related to the quality and/or quantity of the samples or issues related to the assay). Under such circumstances, the number of samples may be inadequate to perform a rigorous data analysis and the available data will only be listed and potentially summarized.

Additional analyses that may be performed after the completion of the end-of-study CSR will be documented in separate reports. These analyses may include but are not limited to the analysis of biomarkers generated from samples collected during the study but analyzed after the database lock and completion of the CSR. The data analysis will be described in an addendum of the SAP or in a stand-alone analysis plan document, as appropriate.

### **2.12.1 Biomarker analysis dataset**

The FAS will be used for all biomarker analysis. Unless otherwise specified, all statistical analyses of biomarker data will be performed on patients with biomarker data.

The distribution of baseline clinical covariates in treatment arms, the demographic and disease characteristics of subjects with available biomarker data may be compared to those of the FAS.

[REDACTED]

[REDACTED]

[REDACTED]

### **2.12.3 List of biomarkers evaluated and the collection time points**

The biomarkers evaluated in the study are listed in [Table 2-7](#) below.

**Table 2-7      Sample biomarker summary table**

Biomarker	Time point	Sample	Method
FLT3 mutation	Screening visit (eligibility)	Bone Marrow Aspirate or Peripheral Blood	PCR-CE

#### **2.12.4   General Data Handling and preprocessing**

Data preprocessing and transformations are described in detail in the Programming Dataset Specification.

The screening assessment (pre-dose) will be used as the baseline value.

[figure not shown]
When more than one biomarker data value are available for a subject at any time point, the mean of the replicate values will be used for all statistical analyses.

Percent change is calculated as  $((\text{visit } i - \text{baseline}) / \text{baseline}) * 100$ . To compute the average percent change from baseline is to compute the average expression level at each time point and then compute the percent change using the average values. Fold change is calculated as the ratio of biomarker value at  $((\text{visit } i) / (\text{Baseline biomarker value}))$ . The number of subjects for the average of percent change from baseline might vary due to potential missing values at respective time points.

#### **2.12.5   Data analysis**

##### **2.12.5.1   FLT3 Mutation**

FLT3 mutation will be identified by analysizing FLT3 gene for either an internal tandem duplication mutation (ITD) or a point mutation in the activating loop of the tyrosine kinase domain (TKD) at baseline. FLT3-ITD mutation will be stratified at ITD allelic ratio  $<0.7$ , ITD allelic ratio  $\geq 0.7$ .

## 2.14 Interim analysis

For part 2, an interim analysis for efficacy will be conducted when 60 patients are randomized and at least 24 EFS events are documented (expected around 14 months from the date of first patient randomized in the study assuming the recruitment period as 14 months). In case that 36 EFS events are documented before randomization completion, the interim analysis can be skipped and Novartis will conduct primary analysis.

At the interim analysis, the study will be considered as a positive result when the following both success criteria are met:

- Criterion 1: estimated HR at interim analysis  $< 1$ .
- Criterion 2: the Bayesian predictive probability of (HR for EFS when 36 EFS events are documented  $< 1$ ) given data up to the data cut off for interim analysis  $> 0.9$ . To calculate the predictive probability, assuming a weakly informative prior distribution derived from Study [\[A2301\]](#) data and the prior distribution will be updated using the available data from patients in the FAS at interim analysis (for more detail of weakly informative prior, refer to [\[study protocol Section 14.1\]](#)).

This interim analysis will be assessed by a DMC, however, even if interim success criteria are met, the study will be continuing blinded to patients, investigators and monitors until the primary analysis and thereafter unblinded. At the final analysis more mature data can be evaluated.

The interim analysis will be performed by an independent statistician and an independent programmer who provides the results to the DMC. The DMC will then be assessing the success criteria. Further details will be described in the DMC charter.

If Health Authorities require to submit the study results after interim analysis but before primary analysis, additional analysis may be performed.

The primary analysis will be performed using the pre-defined cut-off date of 30 November 2020 with the number of EFS events documented by this date. The end of study will occur at the latest 36 months after the start of the study treatment for the last patient. At this time, the final analysis will be performed.

For all of interim, primary and final analyses, the type I error alpha will not be considered because this study will pursue an estimation approach rather than formal hypothesis testing in which the criteria for success is based on the probability of  $HR < 1$  in favor of midostaurin.

ISC will review all available safety data in the part 1 to evaluate whether the trial may advance to the part 2 in Japan. The analyses may be performed by a trial statistician internal to Novartis and their results will be provided to the Independent Safety Committee, when the available data is adequate to perform a data analysis. Details will be described in a separate SAP for the safety review.

### 3 Sample size calculation

#### 3.1 Primary analysis

##### Safety evaluation part (in Japan only)

A minimum of 3 (if no Safety Events) or 6 evaluable Japanese patients will be required to confirm the tolerability of midostaurin in combination with standard chemotherapy in the safety evaluation period. No formal statistical power calculations to determine sample size were performed for this study.

##### Randomization part

This is a bridging study that will support the registration of midostaurin including in Japan. This study will pursue an estimation approach rather than formal hypothesis testing in which the criterion for success is based on the probability of  $HR < 1$  in favor of midostaurin.

As per the initial protocol design (i.e. pre-Amendment 3), the required sample size for the part 2 of the study was determined based on the empirical probability to meet the success criterion. It was assumed that EFS for midostaurin and placebo in A2220 would follow the same survival distributions as observed in study A2301. Consequently all factors which might affect the EFS prolongation e.g., SCT rate in CR1 were also assumed to be the same as in Study A2301. It was also assumed that there was no difference between the two chemotherapy regimens (RATIFY regimen and JALSG regimen).

In order to calculate the probability to meet the success criterion, a simulation study was performed using actual EFS data from Study A2301. To simulate a study, 30 patient observations were randomly selected from each treatment arm of Study A2301 and 30000 studies were simulated. The, median EFS and HR for EFS were calculated for each study. The median EFS in the control arm averaged 5.4 months and in the midostaurin arm 10.3 months. The average hazard ratio was 0.77 (corresponding to a 23% reduction in the hazard rate for EFS), which was similar to estimated HR in Study A2301 of 0.728.

In addition to the above assumptions, assuming that enrollment will continue for approximately 15 months at a uniform rate of 4 patients a month and the primary analysis will occur when 36 EFS events are documented (expected 21 (95%CI: [14.4, 34.2]) months from date of first patient to be randomized), 60 patients will need to be randomized to the two treatment arms in 1:1 ratio to meet the success criterion with a probability of 84.1%.

In addition to the above simulation, another simulation was performed to calculate the probability of success at interim analysis. When the enrollment period will be 14 months considering the currently expected enrollment rate, the probability to meet success criteria at interim analysis (described in [\[study protocol Section 2.14\]](#)) is 78.1% and the time from first patient to be randomized to the interim analysis is expected to be 14.1 (2.5 - 97.5 percentile: [14.0 – 15.4]) months based on same survival distribution as in Study [A2301]. In addition, the conditional probability to meet the success criterion of primary analysis under showing positive result at interim analysis is 96.8%. For more details, please refer to [\[study protocol Section 14.1\]](#).

Based on the overall observed EFS events over time, the rate of discontinuations without EFS event and the predictions of future events, there is a risk that the targeted 36 EFS events will not be observed within a reasonable timeframe. Therefore the primary analysis will be performed using the pre-defined cut-off date of 30 November 2020 with the number of EFS events documented by this date.

As per the current number of patients who are still on follow-up for EFS and the survival distributions of EFS post-induction observed in study [A2301], additional 5 EFS events are expected to be observed until 30 November 2020. The study power would be approximately 82.7% when total 33 EFS events are observed under the original assumptions shown above (that is, EFS for midostaurin and placebo in A2220 would follow the same survival distributions as observed in study [A2301], consequently all factors which might affect the EFS prolongation e.g. SCT rate in CR1 were the same as in Study [A2301], and there was no difference between the two chemotherapy regimens).

### **3.2 Power for analysis of key secondary variables**

Not applicable.

## **4 Change to protocol specified analyses**

In section 2.11 (patient-reported outcomes), the primary PRO variables of interest of QLQ-C30 was changed from total score to the global health status/QoL score to revise to the correct variable.

## **5 Appendix**

### **5.1 Imputation rules**

#### **5.1.1 Study drug**

The following rule should be used for the imputation of the dose end date for a given study treatment component:

**Scenario 1:** If the dose end date is completely missing and there is no EOT page and no death date, the patient is considered as on-going:

The patient should be treated as on-going and the cut-off date should be used as the dose end date.

**Scenario 2:** If the dose end date is completely or partially missing and the EOT page is available:

Case 1: The dose end date is completely missing, and the EOT completion date is complete, then this latter date should be used.

Case 2: Only Year(yyyy) of the dose end date is available and yyyy < the year of EOT date:

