7.1.4 Treatment period

Patients will be assigned on Cycle 1 Day 8 of induction therapy to midostaurin or placebo using a stratified randomization according to FLT3 mutation and treatment regimen.

- Study treatment will begin on Day 1 of Cycle 1 with chemotherapy: daunorubicin from Day 1 to Day 3 or Day 5 and cytarabine from Day 1 to Day 7. Study treatment will continue on Day 8 with midostaurin/placebo until Day 21.
- Chemotherapy and midostaurin/placebo will be administered as indicated in [Table 7-1](#) and until the subject experiences any of the following: persistent disease, relapse as determined by investigator, unacceptable toxicity that precludes further treatment, pregnancy, start of non-protocol anti-cancer therapy, discontinuation at the discretion of the Investigator or patient, loss to follow-up, death, or study termination by the Sponsor.

Visit frequency

- Induction phase cycle 1: assessments will be scheduled 2 times per week until hematology recovery. This cycle may be longer than 28 days (until hematology recovery occurs), and the assessments will be performed accordingly. If the patient has evidence of persistent leukemia on a bone marrow evaluation from Day 21 to Day 28 or at the end of the first induction cycle, then a second cycle of induction therapy will be administered.
- Induction phase cycle 2: assessments will be the same as for Cycle 1, except for the PK [REDACTED] [REDACTED]. For details of assessments in induction Cycles 1 and 2, refer to [Table 7-1](#).
- Patients who achieve a CR will continue with consolidation therapy for up to 4 cycles. In case of toxicities with RATIFY regimen, patients are allowed to have 3 cycles only at the discretion of the investigator. For JALSG regimen, patients will have 3 cycles during consolidation therapy.
- Patients who remain in remission after consolidation therapy will begin continuation therapy for up to 12 cycles of 28 days each. Continuation therapy will begin no sooner than 14 days after the last dose of midostaurin/placebo during the last cycle of consolidation therapy. Patients who remain in remission after 12 cycles of continuation therapy will continue in post-treatment follow-up.

Time windows for scheduling assessments

- Reasonable effort should be made to follow the schedule of assessments as described in the protocol and especially during the induction and consolidation cycles for PK and ECG assessments.

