#### Data included in the analysis

The interim analysis for efficacy were conducted when 60 patients were to be randomized (actual 62 patients) and at least 24 EFS events were documented. In case that 36 EFS events were documented before randomization completion, the interim analysis could be skipped and Novartis would plan to conduct primary analysis.

The primary analysis was performed using a pre-defined cut-off date of 30 November 2020 with the number of EFS events were documented as per amended protocol version 03 (released date 10-Sep-2020) by this date.

The end of study will occur at the latest 36 months after the start of the study treatment for the last patient. At this time, the final analysis will be performed.

All statistical analyses will be performed using all data collected in the database up to the data cutoff date. All data with an assessment date or event start date (e.g., vital sign assessment date or start date of an adverse event) prior to or on the cut-off date will be included in the analysis. Any data collected beyond the cut-off date will not be included in the analysis and will not be used for any derivations.

All events with start date before or on the cut-off date and end date after the cut-off date will be reported as 'ongoing'. The same rule will be applied to events starting before or on the cut-off date and not having documented end date. This approach applies, in particular, to adverse event

and concomitant medication reports. For these events, the end date will not be imputed and therefore will not appear in the listings.

At final analysis the cut-off date means LPLV.

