### **Cumulative dose**

Cumulative dose of a study treatment is defined as the total dose given during the study treatment exposure and will be summarized for each of the study treatment components.

The **planned cumulative dose** for a study treatment component refers to the total planned dose as per the protocol up to the last date of investigational drug administration.

The **actual cumulative dose** refers to the total actual dose administered, over the duration for which the subject is on the study treatment as documented in the DAR eCRF.

For patients who did not take any drug the cumulative dose is by definition equal to zero.

For continuous dosing, the actual cumulative dose is the sum of the non-zero doses recorded over the dosing period and the planned cumulative dose is the planned starting dose summed over the same dosing period.

For intermittent dosing, the actual cumulative dose should be defined based on the days when the subject is assumed to have taken a non-zero dose during dosing periods.

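### SAP 5.1.1 sets a missing dose end date for any component to EOT, 31 December or LPLV with no cap at its dosing days or cycle, so a record can be overstated by weeks to more than a year

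*SAP*

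**What the plan says.** SAP 5.1.1 is headed Study drug, but its scope is wider: "The following rule should be used for the imputation of the dose end date for a given study treatment component". SAP 2.1.1 defines study treatment as daunorubicin, cytarabine or midostaurin/placebo.

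- **Scenario 1** has this trigger: "If the dose end date is completely missing and there is no EOT page and no death date, the patient is considered as on-going". The date is then set by the sentence: "The patient should be treated as on-going and the cut-off date should be used as the dose end date".
- **Scenario 2 (EOT page available).** Its first case reads: "The dose end date is completely missing, and the EOT completion date is complete, then this latter date should be used". A year-only date becomes 31 December if the year precedes the EOT year (Case 2), or the EOT date if the years agree (Case 3). A month-and-year date in an earlier month of the EOT year becomes the month end (Case 4).
- **Other patterns** go to the data manager. The only check after imputation is that the date is not before treatment start.

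This SAP is for the final analysis, and SAP 2.1 adds: "At final analysis the cut-off date means LPLV". On timing it says: "The end of study will occur at the latest 36 months after the start of the study treatment for the last patient".

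Protocol 7.1.4 gives the first-cycle chemotherapy as "daunorubicin from Day 1 to Day 3 or Day 5 and cytarabine from Day 1 to Day 7". Study drug is taken on Days 8 to 21 of induction and consolidation cycles, and on all 28 days of each continuation cycle (Protocol 6.1.1 and Table 6-1).

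**The concern.** The rule suits one drug taken without a break until EOT. Here that describes only study drug in continuation. Chemotherapy and the induction and consolidation study drug come in short blocks, and EOT can follow many cycles later. The rule has a lower bound but no upper bound tied to the block.

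Three things are at stake:

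- **Exposure duration** by cycle and phase, for every component.
- **Chemotherapy cumulative dose and relative dose intensity (RDI).** SAP 2.4.2.1 computes chemotherapy dose intensity as cumulative dose over body surface area per cycle. No duration stands in the denominator, so a dose carried across an over-long record passes straight into RDI.
- **The on-treatment period**, which ends 30 days after the last dose of any component (SAP 2.1.1). This matters if the imputed date feeds that last dose date, which the SAP does not exclude.

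**Working it through.** **Inputs.** Dosing days and doses: Protocol Table 6-1. Consolidation cycles start at least four weeks apart; continuation starts at least 14 days after the last consolidation dose of study drug and lasts up to 12 cycles of 28 days; a second induction starts on Day 24 at the earliest (Protocol 6.1.1). EOT visit within 7 days of stopping (Protocol 7.1.4). 62 randomized (Protocol, Amendment 3), so about 31 per arm.

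**Assumptions.** Shortest compliant timeline unless stated; cycles of 28 to 35 days where a record is truncated; 36 months = 1,096 days; one EOT date per patient.

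**1. Reproduce the SAP's planned dose intensities (JALSG / RATIFY, mg/m² per cycle).** Induction cytarabine: 100 × 7 = 700 / 200 × 7 = 1,400. High-dose cytarabine: 2,000 × 2 × 5 = 20,000 / 3,000 × 2 × 3 = 18,000. Daunorubicin: 50 × 5 = 250 / 60 × 3 = 180. All match, so the SAP itself works from these short dosing blocks.

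**2. Earliest last dose of a completer with one induction.** RATIFY: consolidations start on Days 29, 57, 85 and 113; last consolidation study-drug dose on Day 133; continuation starts on Day 133 + 14 = 147 and ends on Day 147 + 336 − 1 = 482. JALSG (three consolidations): Day 454. With two inductions: Day 505 and Day 477.

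**3. EOT route, record not cut at its cycle.** False days = EOT day − true last dosing day, with EOT on the last dose day (add up to 7 for a later visit).

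| Record with missing end date, completer | False days, range over regimens and one or two inductions |
|---|---|
| Induction 1 daunorubicin | 449–502 |
| Induction 1 cytarabine | 447–498 |
| Induction 1 study drug | 433–484 |
| High-dose cytarabine, last consolidation | 365 |
| Study drug, last consolidation | 349 |
| Study drug, last continuation record | 0 |

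For early stoppers, a missing induction 1 cytarabine date gives, allowing 0 to 7 days to the visit:

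- stop after induction 1 (Day 28): 21–28 days
- stop after induction 2 (Day 51): 44–51 days
- stop after consolidation 4 (Day 140): 133–140 days

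An excess above 365 days for that record needs EOT on Day 7 + 366 = 373 or later. With one induction that is continuation cycle 9 for RATIFY ((373 − 147)/28 = 8.07 cycles done) or cycle 10 for JALSG ((373 − 119)/28 = 9.07).

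**4. EOT route, record cut at its cycle.** SAP 2.4.2.1 counts exposure by cycle as administration days within the cycle. Cut at 28 to 35 days, induction cytarabine is overstated by 28 − 7 = 21 to 35 − 7 = 28 days. RATIFY daunorubicin at 28 days is overstated by 28 − 3 = 25.

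**5. Chemotherapy RDI, if the daily dose is carried across a record cut at 28 days.**

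- RATIFY daunorubicin: 60 × 28 / 180 = 933%
- JALSG daunorubicin: 50 × 28 / 250 = 560%
- RATIFY induction cytarabine: 200 × 28 / 1,400 = 400%

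One such RATIFY daunorubicin record moves that cycle's mean in a 31-patient arm by (933 − 100)/31 = about 27 points.

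**6. Scenario 1 at the final analysis, with LPLV 36 months after that patient's start.** Full courses from step 2: 1,096 − 505 = 591 to 1,096 − 454 = 642 false days, or 19.4 to 21.1 months. With six induction and consolidation cycles stretched to 42 days (assumed): 6 × 42 + 14 + 336 = 602 days, leaving 1,096 − 602 = 494 days, or 16.2 months. Patients who started before the last one would have more.

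**The case against.** The strongest reply is that the SAP elsewhere limits the damage. Induction and consolidation durations are sums of per-cycle counts, so an induction 1 record should not contribute days outside induction 1. This removes much of the error if programmed that way, but an excess of about 3 to 4 weeks on a 3- to 7-day drug remains. The SAP also does not say how a record running past its cycle is handled.

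Four stronger readings are tempting and not supported:

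- **An RDI near 16,000%.** Carrying 60 mg/m² over 482 days gives 60 × 482 / 180 = 161 times the plan. That leans on the statement that "the actual cumulative dose is the sum of the non-zero doses recorded over the dosing period", which SAP 2.4.2.1 confines to continuous dosing. Intermittent dosing rests on days when a dose is assumed taken within dosing periods. The figure is an arithmetic extreme, not an expected value.
- **Impossible study-drug RDI.** Its dose intensity divides cumulative dose by duration. If both run over the same over-long record, the ratio largely cancels.
- **Late deaths counted as on-treatment.** Scenario 1 requires that there is no death date.
- **A materially longer on-treatment window by the EOT route.** With the visit on schedule, the shift is at most 7 days.

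Two further replies stand. Missing values are queried before lock (Protocol 9.4), and neither document reports how many dose end dates are missing. Routine adverse event collection is required only for at least 30 days after the last dose, so there is no planned stream of late events.

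**Conclusion.** The rule is wrong as written for daunorubicin, cytarabine, and induction and consolidation study drug. It is acceptable for the last open continuation record. The size per affected record runs from weeks, if cut at the cycle, to more than a year, if uncut and an early-cycle date is missing in a near-completer. Chemotherapy dose and RDI are distorted only if the daily dose is carried across the record.

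Scenario 1 does not fit a final analysis. With a planned maximum of 18 cycles, nobody should still be on treatment at an LPLV near the 36-month limit. If the scenario were used, the on-treatment window could grow by roughly 16 months or more, less if LPLV came earlier. Follow-up hematology (Protocol 7.1.8) could then enter the worst on-treatment value tables, and late SAEs suspected to be related (Protocol 8.2.2) could count as treatment-emergent. This concerns only patients with neither an EOT page nor a death date, possibly none.

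EFS and OS are not affected through these dates: SAP 2.1.1 bars completely imputed dates, naming this very case, from the last contact date. With the number of missing dates unknown, the practical effect cannot be sized. The correction is worth making because it is cheap.

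**What to change.** - Cap the imputed end date at the earliest of: the component's last protocol-scheduled administration day in that cycle, the day before the next record of that component, the EOT date, the death date and the cut-off.
- Drop the scheduled-day cap only for an open continuation-phase study-drug record, where the EOT date may be used.
- At the final analysis, replace Scenario 1 with the data-query route that SAP 5.1.1 already has for uncovered patterns, with the same cap as fallback.
- State how a record extending past its cycle is treated.

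With the cap, a missing RATIFY induction 1 cytarabine end date gives 7 days, 1,400 mg/m² and RDI 100%.

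The cost is SAP wording and one imputation routine, with no new data. There is a small downside: the cap assumes dosing to the last scheduled day, so it pulls RDI towards 100% and can hide early stopping. Flag imputed records in the listings and report their number by arm.
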